12.1 Analysis population

The study population is divided into the following categories:

- Full Analysis Set (FAS): The set of subjects according to the Intention To Treat (ITT) principle. It refers to the dataset composed of all subjects who participated in the randomization process and underwent baseline assessments. For subjects for whom complete efficacy assessments are not observed, data truncation will be carried out following the Last Observation Carried Forward (LOCF) principle.
- Per-Protocol Set (PPS): It refers to the collection of cases that meet the inclusion criteria, do not meet the exclusion criteria, and complete the treatment regimen. This includes cases that adhere to the study protocol, exhibit good compliance, and complete the specified CRF entries for analysis (PP analysis).
- Safety Set (SS): It refers to the set of all randomized subjects who received the study drug and had at least one safety assessment after baseline.

The efficacy analysis will be conducted based on the FAS and the PPS. The analysis of all baseline demographic data will be conducted based on the FAS, and safety assessment will be performed on the SS.

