12.2 Statistical analysis method

- All statistical tests will be two-sided, and a *P*-value ≤0.05 (two-sided) will be considered statistically significant for the tested differences. (Unless specifically stated otherwise)
- Descriptive analysis: For count data, describe with proportions. For measurement data,

- describe with mean, standard deviation, maximum, and minimum values. For non-normally distributed data, describe with median, 25th percentile, and 75th percentile.
- The comparison of general conditions between the two groups will be analyzed using appropriate methods based on the type of indicator. Inter-group comparisons of quantitative data will be performed using paired t-tests or Wilcoxon rank-sum tests. For categorical data, the chi-square test or exact probability method will be employed. For ordinal data, Wilcoxon rank-sum tests or CMH tests will be used.

12.2.1. Enrollment and study completion:

Summarize the number of enrollments and completions for each center and provide a list of dropouts. Different dataset sizes for each group, distribution of cases in each center, comparison of overall dropout rates, and a detailed list of reasons for termination. Describe the demographic characteristics of patients (age, height, weight, vital signs, etc.), medical history, and medication history. Compare age, height, and weight between the two groups to assess their comparability.

12.2.2. Compliance analysis:

- Medication compliance analysis: Compare whether patients in the two groups use the study drug on time and in the correct dosage, and whether they refrain from using prohibited drugs and foods according to the protocol.
- Concomitant medication analysis: Tally the number of patients in each group using concomitant medications and provide a detailed list.

12.2.3. Efficacy evaluation:

- Baseline: Describe the baseline characteristics of each efficacy indicator. Refer to general methods for inter-group comparisons.
- Primary efficacy endpoints:

Conduct both PP and FAS analyses concurrently. The primary time point for evaluating the proportion of patients with improved modified Rankin (mRS) scores ≤ 1 in terms of activities of daily living is at Day 90 (for the PP population) or at the time of premature discontinuation (for the FAS population). The primary indicator will be compared between the two groups using the CMH- χ^2 analysis method, controlling for center effects.

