Appendix 2: Modified Rankin Scale (mRS)

Modified Rankin Scale is used to measure the functional recovery of patients after stroke. The scale is divided into six levels, and the formal definition of each level is provided in bold below. Italics give further instructions with a view to reducing possible errors among different observers, but there is no requirement for the architecture of the interview. Note that only symptoms occurring since stroke were considered. Patients were considered to be able to walk independently provided they could walk with the aid of certain auxiliary devices without external assistance.

If two levels seem equally applicable to the patient and further questioning is unlikely to lead to an absolutely correct choice, the higher level should be chosen.

Level 0: completely asymptomatic

Although mild symptoms may occur, the patient has not noticed any new functional limitations and symptoms since stroke.

Level 1: Symptomatic, with no significant disability: Able to perform all routine duties and activities.

Patients have certain symptoms caused by stroke, either physically or cognitively (such as affecting speech, reading, writing; or body movement; or sensation; or vision; or swallowing; or emotion), but can continue to engage in all work, social, and leisure activities they have previously engaged in before the stroke. The key question used to distinguish between level 1 and 2 (see below) can be, "Are there things you used to do regularly, but you can't do again after stroke?" Activities more frequently than once a month are considered "frequent".

Level 2: Mild disability: Unable to perform all previous activities but can manage personal affairs without assistance.

Some activities that can be done before stroke (such as driving, dancing, reading, or working) can no longer be performed by people after stroke, but they can take care of themselves daily without assistance. Patients are able to dress, walk, eat, go to the bathroom, prepare simple food, shop, travel locally, etc., without the help of others. Patients do not require supervision in life. It is envisaged that patients at this level can live alone for one week or longer without

the care of others.

Level 3: Moderate disability: Need some assistance, but can walk without assistance.

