At this level, the patient can walk independently (with the aid of auxiliary machinery) and be able to dress independently, go to the bathroom, eat, etc., but need the assistance of others for more complex tasks. For example, need others to perform tasks like shopping, cooking, or cleaning, and visit from others more than once a week to ensure that these activities are completed. What needs assistance is not just caring for the body, but giving advice: for example, patients at this level will need supervision or encouragement to deal with finances.

Level 4: Severe disability: Unable to walk without assistance from others and unable to attend to one's own bodily needs.

Patients need help with everyday life, whether it be walking, dressing, going to the bathroom or eating. Patients need to be cared for at least once a day, usually twice or more, or must live close to the caregiver. To distinguish between level 4 and 5 (see below), consider whether patients can routinely live alone for an appropriate amount of time during the day.

Level 5: Severe disability: bedridden, incontinent, requiring constant nursing care and attention.

Although trained care is not required, it requires caring for several times during the day and night.

Completely asymptomatic		0
Symptomatic	Not very severe, no significant disability; able to perform ordinary tasks or activities	
Mild disability	Lose some capacity, unable to complete all the above actions, but can take care of oneself without assistance from others	2
Moderate disability	Lose most of the capacity, complete many things with assistance from others, but can walk without assistance	3
Moderate to severe disability Unable to walk or take care of oneself without assistance from others		4
Severe disability	Bedridden, incontinent, requiring constant care and attention from others	5

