6.1.1 Full analysis set (FAS)

Full analysis set (FAS) or modified intention-to-treat (ITT): Set of all the patients who underwent randomization, given any treatment, and underwent any posttreatment assessment. When main indexes of curative effect are missing, the set should be supplemented with last observation carried forward (LOCF) on the basis of intention to treat (ITT). Comparability analysis and the missing value of secondary effect indexes don't need data-carry-forward. Take analysis on actual data in FAS.

FAS population is the main population for curative evaluation in this study.

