6.2.4 Efficiency evaluation

Baseline efficiency: Describe the baseline of each curative index, and comparison between groups should be made in accordance with general condition. Modified Rankin (mRS) score is regarded as ranked data, and should be compared with Wilcoxon rank sum test. NIHSS score should be regarded as quantitative data and ranked data (4-7 points, 8-14 points and 15-22 points) for description and comparison; BI score as quantitative data and enumeration data (<85 points, ≥85 points) for description and comparison.

Primary efficiency indexes:

PP analysis and FAS analysis should be performed at the same time; evaluation on patients with modified Rankin (mRS) score≤1 should be mainly conducted ontaken at day 90 day (PP set) and the time for suspending and drop-out (FAS set). Primary indexes should be compared between the two groups with CMH-γ2 method for controlling central effect.

Superiority test is adopted for primary indexes, and the hypotheses under test are as follows:

$$H_0$$
: $\pi_{\text{treatment group}} - \pi_{\text{control group}} \le 0$

$$H_1: \pi_{\text{treatment group}} - \pi_{\text{control group}} > 0$$

$$\alpha = 0.025_{\text{(one-sided)}}$$

The treatment group is superior to control group, if H0 is rejected under α level, or lower limit of 95% Cl for difference of retention rate between the two groups is higher than 0. Take sensitivity analysis on primary efficiency indexes with modified Rankin (mRS) score≤2 points as the limit.

Other secondary indexes can be statistically analyzed in accordance with methods for primary indexes.

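### The mRS has no value for death and missing primary outcomes are carried forward, so a patient last scored 0–1 who then dies would count as a success; the effect on the comparison is probably small

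*Combined protocol and SAP*

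**What the plan says.** - **Scale.** Protocol Appendix 2: "The scale is divided into six levels", numbered 0 to 5. The worst is a living patient: "Level 5: Severe disability: bedridden, incontinent, requiring constant nursing care and attention". No level, category or failure rule for death appears in either document.
- **Missing primary outcome.** SAP 6.1.1: "When main indexes of curative effect are missing, the set should be supplemented with last observation carried forward (LOCF". The same section names the FAS as the main efficacy population. Protocol 12.1: "For subjects for whom complete efficacy assessments are not observed, data truncation will be carried out following the Last Observation Carried Forward (LOCF) principle". Neither exempts death.
- **Time point in the FAS.** Protocol 12.2.3 takes the primary outcome at Day 90 for the per-protocol population, "or at the time of premature discontinuation (for the FAS population". SAP 6.2.4 similarly uses "the time for suspending and drop-out (FAS set".
- **Secondary endpoints.** SAP 6.1.1: "the missing value of secondary effect indexes don't need data-carry-forward"; observed data are analysed. The carry-forward rule in protocol 12.1 is not limited to the primary endpoint.
- **Where deaths do appear.** Protocol 10.4.2 has every death reported as an adverse or serious adverse event. Vascular death, confined to haemorrhagic death and fatal pulmonary embolism, is part of the combined vascular endpoint (protocol 9.1.2, SAP 5.2). Neither route feeds the mRS. Protocol 5.3 treats anyone who does not complete the procedures as a dropout, whatever the reason. SAP Table 7.1.1.2 has no row for death, and the primary shell (Table 7.3.2.1) has only ≤1, >1 and missing.

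**The concern.** Death is the worst functional outcome. A rule that fills a dead patient's Day 90 value with a score taken while alive can turn that outcome into the best one. This happens in the primary endpoint and in the population on which the trial will be judged. If deaths are unequal between arms, the error favours the arm with more of them. The secondary endpoints have the matching problem: depending on which document is followed, a death either disappears or keeps a living score. A rule for deaths chosen after unblinding would be a post hoc decision about the primary endpoint.

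**Working it through.** **Following the rules through.** The scheduled mRS assessments are baseline, Day 7, discharge (Day 21 if the stay is longer) and Day 90. Protocol 8.6 adds an mRS after a potential neurological event, and protocol 5.3 asks for a final assessment at withdrawal. A patient who dies before Day 90 has no Day 90 mRS and no defined value to stand in its place. The only written rule for an absent primary value in the FAS is carry-forward, so the last living score is used. If it is 0 or 1, the patient is a success.

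On secondary endpoints:
- SAP 6.1.1: the death is missing for mRS ≥3, NIHSS response and BI ≥85.
- Protocol 12.1: the death takes its last living score.

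The two FAS definitions also differ. The SAP requires treatment and a post-treatment assessment, so a death before any such assessment is outside its FAS. The protocol requires only randomisation and a baseline assessment.

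**Planned figures.** Protocol 4.2 and SAP 4.4: 40% vs 47%, two-sided α 0.05, power 80%. With pooled variance and mean rate 0.435:

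n = [1.960·√(2×0.435×0.565) + 0.842·√(0.40×0.60 + 0.47×0.53)]² / 0.07² ≈ 786.2, i.e. 787 per arm, as stated. With 20% dropout, 2×787/0.8 = 1,967.5, i.e. 1,968 (984 per arm), as stated.

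**Assumed inputs, not in the documents.** 90-day mortality m = 1–5%; share s of deaths whose last mRS was 0–1 = 10–20%. The one mortality figure in the documents, 10–15% in the protocol Background, is for stroke in general and is not a planning assumption.

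**False successes in one arm = 984·m·s.**
- Low: 984×0.01×0.10 = 0.98, about 1 patient (0.1 points).
- High: 984×0.05×0.20 = 9.84, about 10 patients (1.0 point).

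**Bias in the difference between arms = m_T·s_T − m_C·s_C.**
- Same m and s in both arms: 0. At m = 5%, s = 20% the rates become 41% vs 48%, and power at 787 per arm moves from 80.0% to 79.8%.
- 5% vs 3%, s = 10%: 0.5 − 0.3 = 0.2 points. With both true rates at 40%, the one-sided type I error at 787 per arm is 3.0% against 2.5%.
- Largest in the range, 5% vs 1%, s = 20%: 1.0 − 0.2 = 0.8 points. If the shares also differ: 5%×20% − 1%×10% = 0.9 points.

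For scale, the standard error of the difference at 984 per arm and 40% is √(2×0.40×0.60/984) = 2.21 points, so the 95% half-width is 4.3 points. A bias of 0.8 is 0.36 standard errors, giving a one-sided type I error of P(Z > 1.96 − 0.36) ≈ 5.5%. That case needs about 49 deaths in one arm and 10 in the other.

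Outside the assumed range, 10% vs 5% with s = 20% gives 1.0 point and 6.0% at 787 per arm.

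**Secondary endpoints under the SAP rule**, if missing patients are left out of the percentage base. Let d be the disability rate among survivors. Counting deaths as disabled gives m + (1−m)d, so the reported rate is too low by m(1−d), which is less than m: under 1 to 5 points within an arm. Likewise a survivors' response rate r (NIHSS or BI) is too high by m·r, also less than m.

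**The case against.** - **The plan never says that a death is a missing mRS.** True. The result comes from silence on death plus a literal reading of the carry-forward rule, and an analyst might score deaths as failures by convention. But that would be an undocumented departure from the only rule written down.
- **The last score may be later and worse than the discharge score.** This stands. A death preceded by a recurrent stroke may have an event assessment under protocol 8.6, and a withdrawing patient may have a final assessment. Both would lower s and shrink the effect.
- **The 1.0 point should not be set against the 7-point target.** A reader might infer that the rule can use up a seventh of the planned effect. It cannot be read that way: 1.0 point is inflation within one arm, whereas 7 points is a difference between arms. The comparable figure is at most 0.8–0.9.
- **Mortality is not hidden.** A reader might infer that a harmful effect on survival could pass as neutral or beneficial. The documents do not support this. All deaths are reported as adverse or serious adverse events, SAP Table 7.4.1.1 compares serious adverse events between arms, and SAP 7.3.8 compares vascular death. The functional endpoints can be distorted, but the deaths remain in the trial's reporting.
- **Deaths do not certainly leave the secondary denominators.** The protocol and SAP disagree on carry-forward, and the disability shell (SAP Table 7.3.5.1) does not state its percentage base. What is certain is that neither version counts death as a bad outcome.

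**Conclusion.** The point holds and needs correcting before unblinding. As written, the scale and the carry-forward rule together allow a dead patient to be a primary success in the FAS, and the two documents conflict on what happens to deaths in the secondary endpoints.

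The case for correction rests on the rule giving a wrong result in the primary endpoint, not on a large expected bias. On the assumed mortality and share, the primary comparison shifts by nothing when the arms are alike and by at most 0.8–0.9 points when mortality differs sharply; with similar shares it moves towards the arm with more deaths. Higher mortality or a higher share would enlarge this, and later event or withdrawal scores would reduce it. The per-protocol set is largely unaffected because it requires completed treatment.

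**What to change.** State the following in protocol Appendix 2 and 12.1 and in SAP 5.1, 5.2 and 6.1.1:

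1. Death from any cause by Day 90 is scored mRS 6.
2. It is a failure for mRS ≤1 and for the mRS ≤2 sensitivity analysis, and it counts in mRS ≥3.
3. It is a non-response for the NIHSS endpoint and for BI ≥85.
4. It is the worst category in the ordinal mRS analysis. That analysis is listed only in the synopsis; SAP 5.2 and its tables do not contain it, so it must be added to the SAP for this rule to apply.
5. A score taken before death is never carried forward. Any imputation is limited to patients not known to have died.
6. Randomised, treated patients who die before any post-treatment assessment stay in the FAS, and the two FAS definitions are reconciled.
7. The protocol and SAP give the same missing-data rule for the secondary endpoints.

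Confirm that the CRF records the date of death. The documents require deaths to be reported and death records to be supplied for vascular events, but they do not show a date field.

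The cost is wording and one derivation. Response rates become slightly less favourable. The sample size stays at 787 per arm before dropout and 1,968 in total.

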5.2 Secondary effect index

1. Improvement of neurological deficits (ratio of NIHSS≤1 or improve 4 score or more);

Improvement of neurological deficits (ratio of NIHSS≤1 or improve 4 score or more): It is effective for NIHSS≤1 or reducing 4 points or more; compare the ratio of efficacy and inefficacy and the continuous change of NIHSS between treatment group and control group 90 days after random treatment;

2. Improvement of daily life ability (ratio of BI index ≥85);

Ratio of patients with BI index≥85: BI score≥85 indicates the patient with ability of independent living; compare the ratio of patient with ability of independent living and continuous change of BI between treatment group and control group at 90 days after random treatment;

3. Disability rate (ratio of mRS score \geq 3)

mRS≥3 indicates the patient without self-care ability; compare the disability rate between treatment group and control group at 90 days after random treatment;

4. Continuous change of mRS score

Compare change of mRS score at baseline, 7d, discharge day and 90d between treatment group and control group;

5. Incidence of ischemic cerebrovascular diseases during follow-up period;

Ratio of ischemic stroke or TIA within 90 days after random treatment, or ratio of new ischemic focus detected by MRI during the last visit, and take this kind of patients as a group for evaluation or respective evaluation:

6. Incidence of combined vascular events during follow-up period;

Accumulated ratio of patients having newly combined vascular events within 90 days after random treatment;

Definition of combined vascular events: Include any type of stroke (ischemic stroke and hemorrhagic stroke), TIA, myocardial infarction and vascular death.

Vascular death: Hemorrhagic death or fatal pulmonary embolism of any organ.

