7.3 Efficiency evaluation

7.3.1 Baseline effect indexes

Table 7.3.1.1 Baseline mRS score

		FAS	FAS		PPS	
		Treatment		Treatment	Control	
Item	Index	group	Control group	group	group	
Baseline NIHSS score	N(Missing)					
	Mean(SD)					
	Median					
	Q1,Q3					
	Min, Max					
	Statistics					
	P value					

Table 7.3.1.2 Baseline NIHSS score – as quantitative data

		FAS	PPS		
		Treatment		Treatment	
Item	Index	group	Control group	group	Control group
Baseline NIHSS score	N(Missing)				_
	Mean(SD)				

Study No.: Document No.:

			FAS		PPS	
		Treatment		Treatment		
Item	Index	group	Control group	group	Control group	
	Median				_	
	Q1,Q3					
	Min, Max					
	Statistics					
	P value					

Table 7.3.1.3 Baseline NIHSS score – as ranked data

		FAS		PPS	
		Treatment		Treatment	
Item	Index	group	Control group	group	Control group
Baseline NIHSS score	4-7 points n (%)				
	8-14 points n (%)				
	15-22 points n (%)				
	N (Missing)				
	Statistics				
	P value				

Table 7.3.1.4 Baseline BI score – as quantitative data

		FAS		PPS	_
		Treatment		Treatment	
Item	Index	group	Control group	group	Control group
	N(Missing)				_
Baseline BI score	Mean(SD)				
	Median				
	Q1,Q3				
	Min, Max				
	Statistics				
	P value				

Table 7.3.1.5 Baseline BI score – as enumeration data

		FAS		PPS	
		Treatment		Treatment	
Item	Index	group	Control group	group	Control group
Baseline BI score	<85 points n(%)				
	≥85 points n(%)				
	N (Missing)				
	Statistics				
	P value				
	P value				

7.3.2 Primary effect index - Improvement of daily life ability at 90 days after treatment Table 7.3.2.1 Improvement of daily life ability at 90 days after treatment

		FAS		PPS	
		Treatment		Treatment	_
Item	Index	group	Control group	group	Control group
	≤1 point n(%)				
mRS score at 90 days after	>1 point n(%)				
treatment					
	N (Missing)				
	Statistics				
	P value				
	Rate difference				
	95%CI				

Note: 1. Take CMH- χ^2 test to control central effect

2. Statistical description of baseline mRS score see Table 7.3.1.1

Table 7.3.2.2 Improvement of daily life ability at 90 days after treatment – take mRS=2 as limit

		FAS		PPS	
		Treatment		Treatment	_
Item	Index	group	Control group	group	Control group
	≤2 point n(%)				
mRS score at 90 days after	>2 point n(%)				
treatment					
	N (Missing)				
	Statistics				
	P value				
	95%CI				

Note: 1. Take CMH- χ^2 test to control central effect

2. Statistical description of baseline mRS score see Table 7.3.1.1

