7.3.5 Secondary effect index – disability rate

Table 7.3.5.1 Inter-group comparison of disability rate at 90 days after treatment

		FAS		PPS	
		Treatment		Treatment	
Item	Index	group	Control group	group	Control group
	Without self-care				
	ability n(%)				
Disability rate	With self-care				
	ability n(%)				
	N (Missing)				
	Statistics				
	P value				

Note: mRS≥3 indicates the patient without self-care ability

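### One Day-90 mRS split (0–2 v 3 or more) appears in two SAP tables under different missing-data rules, and no rule says how deaths are scored

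*Combined protocol and SAP*

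**What the plan says.** **The split as support for the primary.** SAP 6.2.4 reads: "Take sensitivity analysis on primary efficiency indexes with modified Rankin (mRS) score≤2 points as the limit". Table 7.3.2.2 ("Improvement of daily life ability at 90 days after treatment – take mRS=2 as limit") sits under 7.3.2, the primary index, and contrasts ≤2 with >2.

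**The split as a secondary index.** The third item in SAP 5.2 reads: "mRS≥3 indicates the patient without self-care ability; compare the disability rate between treatment group and control group at 90 days after random treatment". Table 7.3.5.1 reports it for FAS and PPS.

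**Missing data.** SAP 6.1.1 says of the main index: "When main indexes of curative effect are missing, the set should be supplemented with last observation carried forward (LOCF". For the rest it says: "Comparability analysis and the missing value of secondary effect indexes don't need data-carry-forward. Take analysis on actual data in FAS". Protocol 12.1 applies LOCF to incomplete efficacy assessments and does not separate primary from secondary.

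**Deaths.** Protocol Appendix 2 defines six mRS levels, 0 to 5, with none for death. The BI and NIHSS responder definitions (SAP 5.2, 7.3.3, 7.3.4) do not mention death either. Neither document says how a patient who dies before Day 90 is scored.

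**The concern.** There are two linked problems.

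First, mRS takes whole-number values, so ≤2 and ≥3 are complements and the two tables estimate one quantity. If one table fills gaps by carry-forward and the other drops them, the FAS columns can show different denominators, rates and p-values for the same endpoint. A reader could also count one result twice, as a secondary finding and as support for the primary.

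Second, a patient who has died has no Day-90 mRS, BI or NIHSS. Under the observed-data rule, that patient leaves the denominator, and the worst outcome is not counted as a failure. Unless deaths are balanced, the responder comparison is then distorted. Under LOCF the opposite error is possible: a good score at an early visit can stand as the final result for someone who later died. That reaches the primary endpoint as well.

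**Working it through.** **The plan's own figure.** Inputs from protocol 4.2: 40% v 47%, two-sided α 0.05, power 80%. With the pooled-variance formula, n = [1.960·√(2·0.435·0.565) + 0.842·√(0.40·0.60 + 0.47·0.53)]² / 0.07² = 786.2, so 787 per arm. Then 787/0.80 = 983.75, so 984 per arm and 1,968 in total. Both figures reproduce, and this point does not change them. The documents give no planning figure for the mRS 2/3 split or for mortality, so the inputs below are assumptions.

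**1. Same split, two missing-data rules.** Take 984 per arm with 20% missing at Day 90 (the dropout allowance): 197 missing and 787 observed. Assume observed mRS ≤2 of 60% on control and 65% on treatment. The test is a pooled two-proportion z-test, not stratified by centre.

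| Rule | Disabled, treatment v control | Difference | p |
|---|---|---|---|
| Observed only | 34.9% v 40.0% | 5.1 points | 0.037 |
| LOCF, 40% of missing carried as ≤2 in both arms | 39.9% v 44.0% | 4.1 points | 0.068 |
| LOCF, 35% treatment, 45% control | 41.0% v 43.0% | 2.0 points | 0.36 |
| LOCF, 50% treatment, 35% control | 38.0% v 45.0% | 7.0 points | 0.002 |

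With 5% missing, the same three LOCF scenarios give p = 0.012 to 0.052, against 0.025 observed-only. For one arm with 40% observed disability, LOCF shifts the rate by m·(x − 0.40), where m is the fraction missing and x the fraction of those carried forward as disabled. The limits (x = 0 and 1) are −2 to +3 points at m = 5%, −4 to +6 at 10% and −8 to +12 at 20%.

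**2. Deaths dropped from a responder rate.** Let p be the true dead-or-disabled proportion and d the proportion dead. The observed-only rate is (p − d)/(1 − d). With p = 30% in both arms:

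- d = 4%: 0.26/0.96 = 27.1%
- d = 2%: 0.28/0.98 = 28.6%

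Deaths of 4% treatment v 2% control therefore show a false 1.5-point benefit. Deaths of 2% v 4% show a false 1.5-point harm. Deaths of 2% in both arms give 28.6% v 28.6%, with no bias. If p differs between arms but d is equal, the true difference is only rescaled by 1/(1 − d).

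The loss can also hide a benefit. Let 40% of survivors be disabled in each arm, with deaths of 3% treatment v 6% control. In whole patients out of 984, treatment has 30 dead and 382 of 954 survivors disabled; control has 59 dead and 370 of 925 disabled. With deaths excluded, both rates are 40.0%. With deaths counted, they are 412/984 = 41.9% v 429/984 = 43.6%, a 1.7-point benefit that the observed-only table would miss.

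**3. Level of the rate in one arm.** With 40% disability among survivors, counting deaths gives 0.40·(1 − d) + d: 41.2%, 43.0%, 46.0% and 49.0% at d = 2%, 5%, 10% and 15%. The upper values use the general stroke mortality of 10–15% in protocol section 3, which is background and not a trial assumption.

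**4. One patient traced through.** A patient scores mRS 2 at Day 7 and dies before any later assessment. If LOCF governs Table 7.3.2.2, the patient is a success there. The same patient is missing from Table 7.3.5.1 and from the BI and NIHSS responder tables. Had the Day 7 score been 1, the patient would be a success on the primary endpoint.

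**The case against.** **Conflicting results are not certain.** A reader might infer that the SAP must produce two contradictory answers. The documents do not support that. LOCF for mRS ≤2 follows from its label and table position and is not stated. The tables can part only in the FAS and only where Day-90 mRS is missing. The PPS requires the required CRF content to be complete (SAP 6.1.2), so its columns should agree. This objection stands.

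**The plan does not exclude the dead.** It is silent; the loss follows from applying the observed-data rule literally. Deaths are also visible elsewhere: all are reported as AE/SAE (protocol 10.4.2), and vascular death has an efficacy table. That is only a partial answer, because vascular death is limited to haemorrhagic death and fatal pulmonary embolism (SAP 5.2). A death from pneumonia, which protocol Appendix 7 names as a main cause of death after stroke, would be a failure on no efficacy endpoint.

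**No direction of bias is established.** A reader might infer that the rule favours Tongxinluo. Nothing in the documents says which arm will have more deaths. The exclusions for reduced consciousness, marked limb weakness and short life expectancy (protocol 5.2) should also hold mortality down. This stands.

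**An alternative cut-point is a legitimate check.** It does test dependence on the responder threshold, and the SAP does not claim that it tests missing-data handling. This stands in part: the check adds nothing beyond the disability endpoint already planned.

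**Conclusion.** The point holds in this form: one dichotomy is reported twice under labels to which SAP 6.1.1 attaches different missing-data rules, and deaths have no scoring rule on mRS, BI or NIHSS. The FAS tables can give different results for one endpoint. In the assumed 20%-missing example, the difference is 5.1 points observed-only and 2.0 to 7.0 points under LOCF.

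Dropping deaths creates or hides differences of about 1.5 to 1.7 points in the examples with 2–4% or 3–6% mortality, in either direction. It creates no spurious difference when dead-or-disabled and death rates are both equal. These sizes rest on assumed event rates and an unstratified test.

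The matter mainly affects secondary and supporting results. It touches the primary only through carry-forward of patients who die. It should be corrected, but it does not undermine the sample size.

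**What to change.** 1. In SAP 6.1.1, state that a patient who dies before Day 90 stays in the denominator and counts as failure on every responder endpoint: not mRS ≤1 (the primary), disabled on the mRS 2/3 split, BI <85 and NIHSS non-responder. Say explicitly that this covers deaths before any post-treatment assessment, because the SAP's FAS definition requires such an assessment.
2. Report mRS 0–2 v 3–5 or dead once, as the secondary endpoint in Table 7.3.5.1, under one stated rule for other missing values. Move the rate difference and 95% CI there: Table 7.3.2.2 holds the only CI planned for this split, and Table 7.3.5.1 has none. Then drop the separate presentation as a sensitivity analysis of the primary.
3. Reconcile SAP 6.1.1 with protocol 12.1 on whether LOCF applies to secondary endpoints.

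**Cost.** No new assessments are needed, since deaths are already reported, and the sample size is unchanged. The disability wording in protocol 7.1.2 and 9.1.2 must be aligned, so this is more than an SAP edit. Rates become slightly less favourable in both arms. Vital status may be unknown for some patients lost to follow-up, since withdrawn patients are followed for endpoint events only where possible (protocol 5.3); the SAP should say how they are handled.
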